1. SYNOPSIS

Protocol Title: A randomised, double-blind, parallel group study to evaluate the safety, tolerability and pharmacokinetics of a single dose of GSK2269557 administered via the ELLIPTA™ dry powder inhaler to healthy participants.

Short Title: Double-blind study to evaluate the safety, tolerability and pharmacokinetics of a single dose of GSK2269557 in healthy participants.

Rationale: This is the first study using a new formulation of GSK2269557 in healthy participants. GSK2269557 will be administered via the ELLIPTA™ dry powder inhaler (DPI) formulated in a blend containing 0.4% MgSt (magnesium stearate). The previous formulation contained 0.6% MgSt. Healthy participants are considered appropriate to assess the new formulation since previous studies assessing device and formulation have been conducted in healthy participants. Furthermore no significant differences in the pharmacokinetic (PK) profiles have been observed between healthy participants and chronic obstructive pulmonary disease (COPD) patients. Therefore data derived from this study will inform on the PK profile and systemic exposure expected in patients during Ph2b.

Objectives and Endpoints:

Objectives	Endpoints
Primary	
To assess the pharmacokinetic profile of a single dose of GSK2269557 administered via the ELLIPTA™ DPI to healthy participants.	GSK2269557 plasma concentration data and derived pharmacokinetic parameters including area under the plasma drug concentration versus time curve area under the plasma drug concentration versus time curve from zero to time t, area under the plasma drug concentration versus time curve from zero to 24 hours, area under the plasma drug concentration versus time curve from zero to infinity ($AUC_{(0-t)}$, $AUC_{(0-24)}$, $AUC_{(0-\infty)}$), maximum observed plasma drug concentration (C_{max}), time to maximum observed plasma drug concentration (T_{max}), Concentration at trough (C_{trough}), terminal half-life ($T_{1/2}$), where data allow.
Secondary	
To assess the safety and tolerability of a single dose of GSK2269557 administered via the ELLIPTA™ DPI to healthy participants.	Safety and tolerability of GSK2269557 as assessed by clinical monitoring of: 
 • Vital Signs • Electrocardiogram (ECG)

Objectives	Endpoints
	
 • Spirometry • Laboratory safety data • Adverse events (AEs)

Overall Design: The study is a randomised, double blind, parallel group, single dose study in healthy participants. The study will be conducted at a single centre.

Approximately twelve participants will be randomised to receive a single dose of GSK2269557 750 µg or a single dose of GSK2269557 500 µg. Participants will be randomised to GSK2269557 750 µg or GSK2269557 500 µg in a 1:1 ratio.

Number of Participants: A sufficient number of participants will be screened in order to randomise approximately twelve participants such that six participants complete on the GSK2269557 750 µg treatment group and six participants complete on the GSK2269557 500 µg treatment group. Participants will be replaced if necessary.

Treatment Groups and Duration: Participants will be randomised to receive 750 µg of GSK2269557 or 500 µg of GSK2269557 in a 1:1 ratio.

The study consists of the following visits:

- *Screening:* within 28 days of first dose
- *Treatment Period:*
 - Participants will be admitted on Day -1
 - Study treatment will be administrated on Day 1. Participants will be discharged after completion of all 24h post dose assessments on Day 2 and if there are no safety concerns.
 - On Day 3 and Day 6, participants will return to the study clinic on an outpatient basis, in order to complete the assessments described in the SOA (Section 2).
- *Follow-up:*
 - Participants will receive a telephone call at 10-12 days post dose to ensure there are no AEs to report or safety concerns.

The duration of the study for each participant (including screening and follow-up) will last up to 6 weeks.

2. SCHEDULE OF ACTIVITIES (SOA)

Procedure	Screening (up to 28 days before Day 1)	Treatment Period [Days]					Follow-up (10-12 days post dose)	Notes
		-1	1	2	3	6		
Informed consent	X							
Inclusion and exclusion criteria	X							Recheck clinical status before randomization
Demography	X							
Full physical examination including height and weight	X							
Medical history (includes substance usage and current medical conditions)	X							Substances: Drugs, Alcohol, tobacco and caffeine
Urine pregnancy test (WOCBP only)	X	X						
HIV, Hepatitis B and C screening	X							If test otherwise performed within 3 months prior to first dose of study treatment, testing at screening is not required

Procedure	Screening (up to 28 days before Day 1)	Treatment Period [Days]					Follow-up (10-12 days post dose)	Notes
		-1	1	2	3	6		
Admission to unit		X						
Outpatient visit	X				X	X		
Discharge				X				
Laboratory assessments (include liver chemistries)	X	X		X				
Urine Drug, Alcohol and Smoking breath test	X	X						
12-lead ECG	X		X	X				Screening only: ECG in triplicate Day 1: pre-dose, 5 mins & 6 hrs post- dose Day 2: before discharge
Vital signs	X		X	X				Screening only: blood pressure and pulse in triplicate Day1: pre-dose, 1h and 6h post-dose

Procedure	Screening (up to 28 days before Day 1)	Treatment Period [Days]					Follow-up (10-12 days post dose)	Notes
		-1	1	2	3	6		
Spirometry [FEV1 and FVC] (triplicate)	X		X					Day 1: pre-dose, 30 min post-dose
Brief physical examination		X						
Inhaler training		X						Training conducted by reviewing the Patient Information Leaflet with the participant. Additional training may be conducted at the discretion of the investigator.
Dosing study treatment			X					
AE review			←=====→					
SAE review		←=====→						
Concomitant medication review			X	X	X	X	X	

Procedure	Screening (up to 28 days before Day 1)	Treatment Period [Days]					Follow-up (10-12 days post dose)	Notes
		-1	1	2	3	6		
Pharmacokinetic blood sample			X	X	X	X		Day 1: pre-dose, 5 min and 0.5, 2, 6 and 12 hours post-dose. Day 2: 24 hours post-dose. Day 3: 48 hours post-dose Day 6: 120 hours post dose.

- The timing and number of planned study assessments, including safety and pharmacokinetic assessments may be altered during the course of the study based on newly available data (e.g., for safety purposes or to obtain data closer to the time of peak plasma concentrations) to ensure appropriate monitoring.
- Any changes in the timing or addition of time points for any planned study assessments must be documented and approved by the relevant study team member and then archived in the sponsor and site study files, but will not constitute a protocol amendment. The institutional review board (IRB)/independent ethics committee (IEC) will be informed of any safety issues that require alteration of the safety monitoring scheme or amendment of the ICF.

3. INTRODUCTION

GSK2269557 is a potent and highly selective inhaled Phosphoinositide 3 Kinase delta (PI3K δ) inhibitor being developed as an anti-inflammatory and anti-infective agent for the treatment of inflammatory airways diseases.

3.1. Study Rationale

This is the first study using a new formulation of GSK2269557 in healthy participants. GSK2269557 will be administered via the ELLIPTA™ dry powder inhaler (DPI) formulated in a blend containing 0.4% MgSt (magnesium stearate). The previous formulation contained 0.6% MgSt. Healthy participants are considered appropriate to assess the new formulation since previous studies assessing device and formulation have been conducted in healthy participants. Furthermore no significant differences in the pharmacokinetic (PK) profiles have been observed between healthy participants and chronic obstructive pulmonary disease (COPD) patients. Therefore data derived from this study will inform on the PK profile and systemic exposure expected in patients during Ph2b.

3.2. Background

Phosphoinositide 3-kinase δ (PI3K δ), a lipid kinase expressed predominantly in leukocytes, is a potential therapeutic target for inflammatory conditions such as COPD and asthma. Neutrophils and T cells are the two major inflammatory cell types involved in COPD, and both are targeted by inhibition of PI3K δ [Hatcher, 2011]; [Okkenhaug, 2007]; [Sadhu, 2003].

GSK2269557 has been administered to healthy participants and healthy smokers in previous studies, as follows:

- *Study PII115117 (healthy participants):* single and repeat doses of a nebulised solution of GSK2269557 – daily doses up to 6400 μ g for 7 days.
- *Study PII116617 (healthy smokers):* single and repeat doses of a dry powder formulation (DISKUS DPI) of GSK2269557 – single doses up to 3000 μ g, and daily doses up to 2000 μ g for 14 days.
- *Study 201544 (healthy participants):* single centre, three part, randomised, study to evaluate the safety, tolerability and pharmacokinetics of GSK2269557 administered via the ELLIPTA™ dry powder inhaler (0.6% MgSt formulation) – single doses up to 200 μ g, and daily doses of 200 μ g for 10 days (study completed but not yet reported).
- *Study 205759 (healthy Japanese participants):* single and repeat doses of GSK2269557 administered via the ELLIPTA™ dry powder inhaler (0.6% MgSt formulation) – single doses up to 700 μ g, and daily doses up to 700 μ g for 10 days (study completed but not yet reported).

GSK2269557 was well tolerated across the range of doses tested in all studies.

GSK2269557 has been administered to stable COPD patients, patients experiencing a COPD exacerbation and patients with persistent, uncontrolled asthma:

- *Study PIII15119 (stable COPD patients)*: daily doses of up to 2000 µg GSK2269557 are being administered via the DISKUS DPI for 14 days.
- *Study PIII16678 (patients experiencing a COPD exacerbation)*: daily doses of 1000 µg GSK2269557 are being administered via the DISKUS DPI for 12 weeks.
- *Study 201543 (patients with persistent, uncontrolled asthma)*: daily doses of 1000 µg GSK2269557 are being administered via the DISKUS DPI for 28 days (study completed but not yet reported).

There are also two ongoing studies in the clinical phase, one in patients experiencing a COPD exacerbation and one in patients with activated PI3K delta syndrome (APDS)/ p110 delta-activating mutation causing senescent T cells, lymphadenopathy, and immunodeficiency (PASLI):

- *Study 201928 (patients experiencing a COPD exacerbation)*: daily doses of 1000 µg GSK2269557 are being administered via the DISKUS DPI for 12 weeks.
- *Study 204745 (patients with APDS/PASLI)*: daily doses of 700µg GSK2269557 are being administered via the ELLIPTA dry powder inhaler.

More information about the non-clinical and clinical studies is available in the Investigator's Brochure (IB) [GlaxoSmithKline Document Number [2012N141231_06](#)].

3.3. Benefit/Risk Assessment

More detailed information about the known and expected benefits and risks and reasonably expected adverse events of GSK2269557 may be found in the Investigator's Brochure (IB) [GlaxoSmithKline Document Number [2012N141231_06](#)].

3.3.1. Risk Assessment

Potential Risk of Clinical Significance	Summary of Data/Rationale for Risk	Mitigation Strategy
Investigational Product (IP) [GSK2269557]		
Bronchospasm	A general risk with all Inhaled treatments	
Study treatment will be administered in the clinical pharmacology unit in the presence of trained clinical staff.
 
Treat immediately with a short-acting inhaled bronchodilator.
 
Participants will be withdrawn from the study.

Mucosal irritancy	Detected in 13 week toxicology study in the dog	Participants will be monitored for AEs. Thus far this has not been seen in clinical studies.
Unknown risks to an embryo, foetus or nursing infant	There are no studies with GSK2269557 in pregnant or lactating women.	
As specified in the protocol:
 
 • Women who are pregnant, lactating or are planning on becoming pregnant during the study are not eligible to participate. • If a female participant becomes pregnant during the study, she must let the study doctor know immediately. • For women of reproductive potential, a pregnancy test will be performed at Screening and Day-1. • Male participants with female partners of reproductive potential must use highly effective contraception methods to avoid pregnancy while in this study.

3.3.2. Benefit Assessment

Healthy participants participating in this study will receive no direct medical benefit. They might benefit from the thorough medical examination and assessments they receive during the course of the study.

3.3.3. Overall Benefit: Risk Conclusion

Taking into account the measures taken to minimize risk to participants participating in this study, the potential risks identified in association with GSK2269557 are considered justified.

4. OBJECTIVES AND ENDPOINTS

Objectives	Endpoints

Primary
 
 To assess the pharmacokinetic profile of a single dose of GSK2269557 administered via the ELLIPTA™ DPI to healthy participants. 	
 GSK2269557 plasma concentration data and derived pharmacokinetic parameters including area under the plasma drug concentration versus time curve area under the plasma drug concentration versus time curve from zero to time t, area under the plasma drug concentration versus time curve from zero to 24 hours, area under the plasma drug concentration versus time curve from zero to infinity ($AUC_{(0-t)}$, $AUC_{(0-24)}$, $AUC_{(0-\infty)}$), maximum observed plasma drug concentration (C_{max}), time to maximum observed plasma drug concentration (T_{max}), Concentration at trough (C_{trough}), terminal half-life ($T_{1/2}$), where data allow.

Secondary
 
 To assess the safety and tolerability of a single dose of GSK2269557 administered via the ELLIPTA™ DPI to healthy participants. 	
 Safety and tolerability of GSK2269557 as assessed by clinical monitoring of: 
 Vital Signs Electrocardiogram (ECG) Spirometry Laboratory safety data Adverse events (AEs)

5. STUDY DESIGN

5.1. Overall Design

This is a randomised, double-blind, parallel group, single centre study to evaluate the safety, tolerability and pharmacokinetics of a single dose of GSK2269557 administered via the ELLIPTA™ dry powder inhaler to healthy participants.

Eligible participants will be admitted on Day -1 and receive GSK2269557 on Day 1. Participants will be discharged after completion of all 24 h post dose assessments on Day 2 and if there are no safety concerns.

On Day 3 and Day 6, participants will return to the study clinic on an outpatient basis.

Participants will receive a telephone call at 10-12 days post dose to ensure there have been no safety issues since discharge.

The duration of the study for each participant (including screening and follow-up) will last up to 6 weeks.

5.2. Number of Participants

A sufficient number of healthy participants will be screened in order to randomise approximately twelve participants such that six participants on the GSK2269557 750 µg treatment group and six participants on the GSK2269557 500 µg treatment group complete the final sampling timepoint (120 hours post-dose).

An evaluable participant is a participant who takes at least one dose of study treatment and for whom a pharmacokinetic sample was obtained and analysed.

If participants prematurely discontinue the study, additional replacement participants may be recruited and assigned to the same treatment at the discretion of the Sponsor in consultation with the investigator.

5.3. Participant and Study Completion

A participant is considered to have completed the study if he/she has completed all phases of the study including the Follow Up Phone Call.

The end of the study is defined as the date of the last visit of the last participant in the study.

5.4. Scientific Rationale for Study Design

This is the first study that GSK2269557 will be administered via the ELLIPTA DPI formulated in a blend containing 0.4% MgSt. Magnesium stearate has been reduced in this final formulation from that studied in previous trials and has resulted in a change in the respirable mass of the drug product. It is anticipated that this will impact the PK profile in man and resulting in an increase in systemic exposure. Cmax may increase, by an average of approximately 50%-70% compared to the previously studied MgSt containing formulation. The final sampling timepoint (120 hours post-dose) has been

selected to confirm the terminal half-life based on preliminary data from study 205759 in healthy Japanese participants which has shown a half-life of approximately 46 hours.

This study will inform on the exposure of GSK2269557 administered via the ELLIPTA DPI formulated in the new blend containing 0.4% MgSt. Previous studies conducted across healthy participants and patients have shown no major differences in exposure.

5.5. Dose Justification

This study is planned to test two separate dose strengths, 750 and 500 µg via a single dose of GSK2269557. Higher doses of other formulations of GSK2269557 as well as longer treatment duration have been tested in previous healthy participant studies: twice daily doses of 3200 µg were tested as a nebulised solution in healthy participants for 7 days; and daily doses of 2000 µg were tested using the DISKUS DPI in healthy smokers for 14 days and in healthy non-smokers for 10 days at a once daily dose of 200 µg using the ELLIPTA DPI containing 0.6% magnesium stearate (preliminary data, not reported yet). For more detailed information, see the GSK2269557 IB [GlaxoSmithKline Document Number [2012N141231_06](#)].

This is the first study that GSK2269557 will be administered via the ELLIPTA DPI formulated in a blend containing 0.4% MgSt. The change in formulation is expected to increase systemic exposure by up to 50% based on an observed increase in respirable mass as measured by *in vitro* drug product performance (Aerodynamic Particle Size Distribution).

Table 1 below shows the expected multiples of the predicted clinical exposure following a single inhalation of 750 µg or 500 µg compared to both pre-clinical margins and in relation to previously observed clinical exposure. The number presented is the most conservative estimate of cover using the highest exposed individual within study 201544 and compared to the expected geometric mean value derived from pre-clinical data (rat 3 month no observed adverse effect level [NOAEL] exposures) as well as the data from the highest exposed clinical data to date (PII115117; 7 days dosing bid of 3200 µg nebulised GSK2269557 to steady-state).

Table 1 GSK2269557 Systemic Exposure Margins to Pre-Clinical Safety and Clinical Data Following Administration via ELLIPTA DPI Containing Either 0.4% Magnesium Stearate

Dose	Parameter ¹	Exposure Margin	
		Pre-clinical ²	Clinical ³
500 µg	C _{max} (ng/mL)	17	2.0
500 µg	AUC _{0-24h} (ng.h/mL)	23	6.9
750 µg	C _{max} (ng/mL)	11	1.4
750 µg	AUC _{0-24h} (ng.h/mL)	15	4.6

1. Using the highest measured exposed individual based on study 201544 (200 µg top dose) to generate (linear extrapolation including an increase of 1.71 fold for Cmax and 1.54-fold on AUC) the most conservative multiple for either a 500 µg or a 750 µg single dose based on Day 1 data. Cmax and AUC0-24h of 2.6 ng/mL and 12.4 ng.h/mL for 500 µg and a Cmax and AUC0-24h of 3.9 ng/mL and 18.6 ng.h/mL for 750 µg respectively.
2. Based on the NOAEL derived from the rat 3 month toxicology study R29876 with a Cmax and AUC of 43.7 ng/mL and 286 ng.h/mL respectively.
3. Based on the highest achieved geometric mean value derived from reported trials to date of 5.3 ng/mL and 85 ng.h/mL based on exposure on Day 7 following repeat daily single doses.

Based on the above calculations the exposure following a single 750 µg inhaled dose is expected to be well within pre-clinical safety margins and in addition is expected to be lower than the maximum exposure seen to date in reported studies with no adverse events of note associated with that clinical systemic exposure.

6. STUDY POPULATION

Prospective approval of protocol deviations to recruitment and enrolment criteria, also known as protocol waivers or exemptions, is not permitted.

6.1. Inclusion Criteria

Participants are eligible to be included in the study only if all of the following criteria apply:

Age

1. Participant must be 18 to 75 years of age inclusive, at the time of signing the informed consent.

Type of Participant

2. Participants who are overtly healthy as determined by medical evaluation including medical history, physical examination, laboratory tests, and ECG tests. Re-screening will be allowed once, at the discretion of the Principal Investigator in consultation with GSK medical monitor (see Section 6.4).
3. Normal spirometry at Screening forced expiratory volume in 1 second (FEV1) and forced vital capacity (FVC) $\geq 80\%$ of predicted – measurements to be taken in triplicate and the highest value for each component must be $\geq 80\%$ of predicted).

Weight

4. Body weight ≥ 50 kg and body mass index (BMI) within the range 18.0 – 35.0 kg/m² (inclusive).

Sex

5. Male or female

a. Male participants:

A male participant must agree to use contraception as detailed in [Appendix 2](#) of this protocol during the treatment period for at least 5 half-lives + 90 days after the last dose of study treatment and refrain from donating sperm during this period.

b. Female participants:

A female participant is eligible to participate if she is not pregnant (see [Appendix 2](#)), not breastfeeding, and at least one of the following conditions applies:

(i) Not a woman of childbearing potential (WOCBP) as defined in [Appendix 2](#)

OR

(ii) A WOCBP who agrees to follow the contraceptive guidance in [Appendix 2](#) during the treatment period for at least 5 half-lives + 90 days after the last dose of study treatment .

Informed Consent

6. Capable of giving signed informed consent as described in [Appendix 3](#) which includes compliance with the requirements and restrictions listed in the informed consent form (ICF) and in this protocol.

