6.2. Exclusion Criteria

Participants are excluded from the study if any of the following criteria apply:

Medical Conditions

1. Asthma or a history of asthma (except in childhood, which has now remitted)
2. Significant history of or current cardiovascular, respiratory, hepatic, renal, gastrointestinal, endocrine, hematological, or neurological disorders capable of significantly altering the absorption, metabolism, or elimination of drugs; constituting a risk when taking the study treatment; or interfering with the interpretation of data
3. Abnormal blood pressure [as determined by the investigator]
4. Alanine transaminase (ALT) >1.5x upper limit of normal (ULN)
5. Bilirubin >1.5xULN (isolated bilirubin >1.5xULN is acceptable if bilirubin is fractionated and direct bilirubin <35%).
6. Current or chronic history of liver disease, or known hepatic or biliary abnormalities (with the exception of Gilbert's syndrome or asymptomatic gallstones)
7. Corrected QT interval (QTc) >450 msec

NOTES:

- The QTc is the QT interval corrected for heart rate according to Bazett's formula (QTcB), Fridericia's formula (QTcF), and/or another method, machine-read or manually over-read.
- The specific formula that will be used to determine eligibility and discontinuation for an individual participant should be determined prior to initiation of the study. In other words, several different formulae cannot be used to calculate the QTc for an individual participant and then the lowest QTc value used to include or discontinue the participant from the trial.
- For purposes of data analysis, QTcB, QTcF, another QT correction formula, or a composite of available values of QTc will be used as specified in the Reporting and Analysis Plan (RAP).

Prior/Concomitant Therapy

8. Past or intended use of over-the-counter or prescription medication including herbal medications within 7 days prior to dosing. Specific medications listed in Section 7.7 may be allowed.
9. Live vaccine(s) within 1 month prior to screening, or plans to receive such vaccines during the study

Prior/Concurrent Clinical Study Experience

10. Participation in the study would result in loss of blood or blood products in excess of 500 mL within 56 days
11. Exposure to more than 4 new chemical entities within 12 months prior to the first dosing day

Consider adding the following criteria if participants can only be enrolled once per study.

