9.3.4. Spirometry

- The maximal amount of air forcefully exhaled in 1 second (FEV1) and forced vital capacity (FVC) will be measured using a spirometer at the time indicated in the SoA.
- FEV1 and FVC measurements will be repeated until three technically acceptable measurements (within 150 mL of each other) have been made. Only the best 3 measurements of each component will be recorded in the electronic case report form (eCRF).
- A full description of the timing and conduct of spirometry procedures will be provided in the study reference manual (SRM).

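### Inclusion 3 defines normal spirometry without the FEV1/FVC ratio, so unrecognised airflow obstruction can be classed as normal

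*Protocol*

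**What the plan says.** Inclusion 3 in Protocol 6.1 opens with "Normal spirometry at Screening forced expiratory volume in 1 second (FEV1) and forced vital capacity (FVC") and sets both at 80% of predicted or more. The rule for applying it is that readings are taken in triplicate and "the highest value for each component must be" at or above that threshold. Each component is judged on its own.

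Protocol 9.3.4 describes the measurement: "FEV1 and FVC measurements will be repeated until three technically acceptable measurements (within 150 mL of each other) have been made". The SAP (10.4.1) takes the maximum FEV1 and maximum FVC at each time point, and its Tables 2.16 and 2.17 summarise values and changes from baseline. Neither document derives or uses FEV1/FVC.

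Other criteria bear on airway disease:

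- Inclusion 1: "Participant must be 18 to 75 years of age inclusive, at the time of signing the informed consent".
- Inclusion 2: participants must be "overtly healthy as determined by medical evaluation including medical history, physical examination, laboratory tests, and ECG tests". Spirometry is not among the items named.
- Exclusion 1: asthma, past or present, but childhood asthma that has remitted is allowed.
- Exclusion 2: significant past, or current, respiratory disorder that could alter drug handling, add risk or disturb interpretation. It gives no spirometric threshold.
- Exclusion 19: current smokers, smoking within 6 months of Screening, or more than 5 pack-years.

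Bronchospasm is the first risk in the table in Protocol 3.3.1, described as "A general risk with all Inhaled treatments".

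**The concern.** Airflow obstruction shows as an FEV1 that is low relative to FVC. Two separate 80% thresholds cannot detect it when FVC is average or high, so the criterion does not test what its title claims. It is also the only criterion in the protocol with a spirometric threshold. The Day 1 pre-dose reading carries no acceptance value.

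Three things are at stake, all modest. First, the listed mitigations for bronchospasm (supervised dosing, treatment, withdrawal) act at or after dosing, so screening is the only step that could select on airway status before the first use of the 0.4% magnesium stearate blend. Second, the report will describe participants as healthy with normal spirometry. Third, spirometry is a secondary safety endpoint summarised by arm, and each arm has six participants.

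**Working it through.** **Inputs from the documents.** Threshold: FEV1 and FVC each at least 80% of predicted (Protocol 6.1). Six participants per arm; between-participant SDs on the log scale of 0.346 for Cmax and 0.382 for AUC(0-24) (Protocol 10.1).

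**Inputs assumed.** Predicted FEV1/FVC from 0.70 to 0.85, and 0.70 as an illustrative cut-off for obstruction. Neither is in the documents.

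**The plan's own calculation.** The half-width of the 90% confidence interval is t(0.95, 5 df) × SD / √6:

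- Cmax: 2.015 × 0.346 / 2.449 = 0.285
- AUC(0-24): 2.015 × 0.382 / 2.449 = 0.314

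Both match Protocol 10.1. The point below does not change them.

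**What inclusion 3 lets through.** FEV1/FVC = predicted ratio × (FEV1 % predicted ÷ FVC % predicted). With FEV1 at 80% and FVC at 100%, the multiplier is 80/100 = 0.80 whatever the predicted ratio. With FVC at 110% it is 80/110 = 0.727. Both combinations pass. The last column is predicted ratio × 80 / 0.70.

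| Assumed predicted ratio | FEV1 80%, FVC 100% | FEV1 80%, FVC 110% | With FEV1 at 80%, ratio is under 0.70 once FVC exceeds |
|---|---|---|---|
| 0.70 | 0.56 | 0.51 | 80.0% |
| 0.75 | 0.60 | 0.55 | 85.7% |
| 0.80 | 0.64 | 0.58 | 91.4% |
| 0.85 | 0.68 | 0.62 | 97.1% |

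The multiplier of 0.80 needs no assumption. The absolute ratios and the comparison with 0.70 do. The documents give no lower limit of normal, so no comparison with one is possible here; a limit set anywhere above 0.80 of the predicted ratio would fail the participant in the second column.

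**Weight in the summaries.** One participant is 1/6 of an arm. If that participant's change in FEV1 differs from the others' mean by d, the arm mean moves by d/6. As an illustration only, taking d equal to the 150 mL repeatability tolerance in Protocol 9.3.4 gives 150/6 = 25 mL.

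**The case against.** The strongest reply is that the protocol already screens for airway disease by other means. Exclusion 2 covers current respiratory disorders, not only diagnosed history. The list in inclusion 2 is introduced as non-exhaustive. Protocol 9 requires all screening evaluations to be reviewed, so the investigator sees FEV1 and FVC together, and the Schedule of Activities calls for a recheck of clinical status before randomisation. Exclusion 19 removes most smokers. This stands, and it rules out a stronger reading that a reader might make: that an obstructed participant meets every criterion unless the disease is already known. An investigator may exclude on judgement. What remains is that no rule requires it, and inclusion 3 has already labelled the result normal.

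A reader might also infer that such participants would inflate PK variability. The documents do not support that. Protocol 3.1 reports no significant difference in PK profiles between healthy participants and COPD patients, and Protocol 5.4 reports no major exposure differences across healthy participants and patients. On the protocol's own account, mild unrecognised obstruction is a weak threat to the primary endpoint.

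Nor do the documents show an excess bronchospasm risk in obstructed participants. Protocol 3.2 lists dry powder dosing in COPD and in uncontrolled asthma at up to 2000 µg and 1000 µg daily, against a single 500 or 750 µg dose here. Those studies used another device, so they do not settle the question, but they count against treating the risk as established. Similar systemic exposure, for its part, says nothing about local airway reactivity.

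**Conclusion.** The point holds as a defect of definition. A criterion presented as normal spirometry accepts an obstructive pattern, and no other criterion supplies a spirometric test for it. The gap is confined to unrecognised obstruction, for example in older participants or after remitted childhood asthma.

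Its size is minor. The documents give no prevalence, and with about 12 participants and the other exclusions there may be few affected or none. The analyses are descriptive, individual spirometry is listed, and no design figure moves. The justification is better safety selection and an accurate label, with a small gain for the spirometry summaries. It does not rest on protecting the PK results.

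**What to change.** Add one clause to inclusion 3: FEV1/FVC, calculated as the highest screening FEV1 over the highest screening FVC, must be at or above the lower limit of normal from the same reference equations used for percent predicted. Name those equations in the protocol or the Study Reference Manual.

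State a single rule. A clause satisfied by either the lower limit of normal or a fixed 0.70 would let the easier limb decide: at an assumed predicted ratio of 0.85, FEV1 85% with FVC 100% gives 0.85 × 0.85 = 0.72 and passes on 0.70 regardless of the age-specific limit. A fixed 0.70 alone errs the other way in older participants: at an assumed predicted ratio of 0.70, someone exactly at predicted sits on the boundary.

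The cost is one clause, one derived value and a few more screen failures. No new procedure is needed, because the screening readings are already taken.
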